### 5.4.3 Exploratory Efficacy Endpoints

#### 5.4.3.1 Prostate-specific Antigen Analysis (Advanced Prostate Cancer)

For the Advanced Prostate Cancer participants, descriptive statistics will be used to evaluate PSA at each timepoint. The absolute and percent changes from baseline will be summarized at each timepoint.

#### 5.4.4 Subgroup Analyses

Efficacy endpoints (CBR, ORR, CD8 conversion) may be presented by tumor type if a tumor type has at least 5 participants enrolled in a treatment group.

### 5.5 Biomarker Analysis

Biomarker exploratory analyses will be determined based on study outcomes and further described in a translational analysis plan.

## 5.6 Safety Analysis

The safety analysis will be based on the Safety Population, which comprises all participants who receive at least one dose of study drug. Participants will be analyzed according to the study intervention actually received.

Safety and tolerability will be assessed through AEs, clinical laboratory parameters, vital signs, and ECGs.

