2.2.1 Immune Checkpoint Inhibitors

Immune checkpoint inhibitors, such as ipilimumab and nivolumab, have resulted in remarkable clinical benefits, including durable clinical responses and improved survival, in several tumor types. However, despite this important advancement, the benefit of immuno-oncology is limited to a minority of patients and only in a few indications. For example, following treatment with a programmed cell death-1 (PD-1) antibody, 31% to 34% of advanced melanoma patients (Weber et al, 2015; Robert et al, 2015), 19% to 20% of non-small cell lung cancer (NSCLC) patients (Borghaei et al, 2015; Brahmer et al, 2015; Herbst et al, 2016), and 25% of renal cell carcinoma (RCC) patients (Motzer et al, 2015) have durable objective (partial or complete) responses and improved overall survival (OS) compared with conventional therapies. Ipilimumab, a human monoclonal antibody (mAb) that blocks cytotoxic T-lymphocyte-associated antigen-4 (CTLA-4) on T cells (approved in 2011), achieves durable clinical responses in ~10% of patients with advanced melanoma and 5-year OS rates of ~18% (Hodi et al, 2010; Schadendorf et al, 2015; Maio et al, 2015). Both nivolumab and pembrolizumab, which are anti-PD-1 mAbs (approved in 2014), achieve clinical responses in 31% to 34% of advanced melanoma patients, and most responses are durable (Weber et al, 2015; Robert et al, 2015). While the activity observed with single-agent anti-PD-1 mAbs is significant, combined treatment with ipilimumab and nivolumab (approved in 2015) results in clinical

[figure not shown]
responses of 55% to 60% in metastatic melanoma patients (Ribas et al, 2017; Larkin et al, 2015). Similarly, nivolumab plus ipilimumab also showed significantly higher ORR compared with sunitinib (42% vs 27%) in previously untreated advanced RCC patients (Motzer et al, 2018). However, the improvement in clinical activity achieved with nivolumab in combination with ipilimumab is accompanied by increased side effects; Grade 3 or 4 events occurred in 59% of patients in the nivolumab plus ipilimumab group, in 21% of those in the nivolumab group, and in 28% in the ipilimumab group (Wolchok et al, 2017). Thus, there is a critical need for biomarkers that can predict which cancer patients will benefit from ipilimumab and nivolumab combination therapy.

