6.1 STUDY INTERVENTION(S) ADMINISTERED

The study interventions to be administered in this study are summarized in [Table 6](#).

Table 6: Study Intervention

Study Intervention Name	Dosage Formulation	Unit Dose Strength(s)	Dosage Level(s)	Route of Administration	Sourcing
Advanced Metastatic Cancer					
Nivolumab	Aqueous solution	10 mg/mL	360 mg (administered with ipilimumab) 480 mg (maintenance)	Intravenous	Bristol-Myers Squibb
Ipilimumab	Aqueous solution	5 mg/mL	1 mg/kg (administered with nivolumab)	Intravenous	Bristol-Myers Squibb
Advanced Prostate Cancer					
Nivolumab	Aqueous solution	10 mg/mL	1 mg/kg (administered with ipilimumab) 480 mg (maintenance)	Intravenous	Bristol-Myers Squibb
Ipilimumab	Aqueous solution	5 mg/mL	3 or 5 mg/kg (administered with nivolumab)	Intravenous	Bristol-Myers Squibb

Participants with $\geq 15\%$ CD8 cells in their tumor biopsy enrolled on the CD8 high arm will be treated with single-agent nivolumab until disease progression. Additionally, participants enrolled on the CD8 high arm in this study could, at disease progression, cross-over to the CD8 low arm; participants with advanced prostate cancer enrolled under Amendment 3+ who cross-over to the CD8 low arm will be placed in Prostate Cohort A.

Nivolumab monotherapy and nivolumab in combination with ipilimumab will be administered as described below.

- *Nivolumab monotherapy (Advanced Metastatic Cancer and Advanced Prostate Cancer):* Nivolumab will be administered at 360 mg as an IV infusion over approximately 30 minutes Q3W \pm 3 days (see [Section 4.3.1](#)). Participants who

continue to show clinical benefit after the first disease assessment will receive nivolumab maintenance 480 mg IV Q4W \pm 3 days until PD or intolerable toxicity (starting at Cycle 5).

- ***Nivolumab in combination with ipilimumab (Advanced Metastatic Cancer):***

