8.3 ADVERSE EVENTS AND SERIOUS ADVERSE EVENTS

The definitions of an AE or SAE can be found in [Appendix 5](#).

Investigators will seek information on AE at each participant contact. AEs reported by the participant (or, when appropriate, by a caregiver, surrogate, or the participant's legally authorized representative) or noted by study personnel will be recorded in the participant's medical record and on the Adverse Event eCRF page.

The Investigator and any qualified designees are responsible for detecting, documenting, and recording events that meet the definition of an AE or SAE and remain responsible for following up AEs that are serious, considered related to the study intervention or study procedures, or that caused the participant to discontinue the study intervention (see [Appendix 5](#)).

8.3.1 Time Period and Frequency for Collecting AE, SAE, and Other Reportable Safety Event Information

All AEs and SAEs will be collected from the time the participant signs informed consent until 100 days after the last dose of study intervention.

Prior to initiation of study intervention, only AEs and SAEs that are related to a protocol-mandated intervention, including those that occur prior to assignment of study procedures (eg, screening invasive procedures, such as biopsies) should be reported. After obtaining informed consent, but prior to initiation of study intervention, other medical occurrences will be recorded as medical history.

If the Investigator learns of any SAE, including a death, at any time after the end of the AE reporting period, and he/she considers the event to be reasonably related to the study intervention or study participation, the Investigator must promptly notify the Sponsor or its designee. The Investigator should report these events directly to the Sponsor or its designee, either by faxing or emailing the Serious Adverse Event Report Form (SAE Report Form).

The method of recording and reporting of AE and SAE are provided in [Appendix 5](#). The procedure for submitting SAE reports is provided in [Section 8.3.8.2](#).

The method of reporting all deaths are provided in [Appendix 5](#).

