8.3.7 Trial-limiting Toxicity

Trial-limiting toxicity (TOX) is defined as the occurrence of any adverse event leading to treatment discontinuation that is possibly, probably, or definitely related to nivolumab, ipilimumab, or ipilimumab in combination with nivolumab during the initial 12 weeks of treatment, unless there is a clear alternative explanation. Additional discontinuation criteria regarding the advanced prostate cohorts can be found in [Section 6.6.1.4](#).

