## 3 STUDY DESIGN

This is an open-label, exploratory study to evaluate nivolumab with or without ipilimumab, with treatment assigned based on the percentage of tumoral CD8 cells at the time of treatment in participants with varying advanced solid tumors.

After consenting to participate in this clinical trial, participants will undergo a tumor biopsy. The tumor tissue will be sent to a Clinical Laboratory Improvement Amendment (CLIA)- and College of American Pathologists (CAP)-certified Immunohistochemistry and Image Analysis Laboratory to determine the percentage of tumoral CD8 cells. Participants will be assigned an immunotherapy regimen according to the percentage of CD8 cells in their tumor biopsies.

There are two distinct cohorts enrolled in this study.

- **Advanced Metastatic Cancer**: enrolled participants with varying advanced solid tumors.
  - Participants with  $\geq 15\%$  CD8 cells in their tumor biopsies (ie, CD8 high tumors) will be treated with nivolumab 360 mg every 3 weeks (Q3W) for 4 cycles, followed by nivolumab maintenance 480 mg every 4 weeks (Q4W). At the time of disease progression, participants may crossover to the CD8 low arm or discontinue treatment.
  - Participants with  $< 15\%$  CD8 cells in their tumor biopsies (ie, CD8 low tumors) will be treated with nivolumab 360 mg Q3W and ipilimumab 1 mg/kg Q3W for 2 doses and then every 6 weeks (Q6W) for 2 doses, followed by nivolumab maintenance 480 mg Q4W.
- **Advanced Prostate Cancer (Protocol Amendment 3)**: enrolled participants with advanced prostate cancer.
  - Participants with  $\geq 15\%$  CD8 cells in their tumor biopsies will be treated with nivolumab 360 mg Q3W for 4 cycles, followed by nivolumab maintenance

480 mg Q4W. At the time of disease progression, participants may crossover to the advanced prostate cohort CD8 low arm of ipilimumab 3 mg/kg and nivolumab 1 mg/kg or discontinue treatment.

- Participants with < 15% CD8 cells in their tumor biopsies (ie, CD8 low tumors) will be randomly allocated into 1 of 2 treatment arms using different doses of ipilimumab.
  - Prostate Cohort A: nivolumab 1 mg/kg Q3W and ipilimumab 3 mg/kg Q6W for 2 cycles, then nivolumab maintenance 480 mg Q4W until disease progression or intolerable toxicity.
  - Prostate Cohort B: nivolumab 1 mg/kg Q3W and ipilimumab 5 mg/kg Q6W for 2 cycles, then nivolumab maintenance 480 mg Q4W until disease progression or intolerable toxicity.

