### 5.6.2 Adverse Events

All reported AEs will be coded using a recent version of the Medical Dictionary for Regulatory Activities (MedDRA) and graded using the NCI Common Terminology Criteria for Adverse Events (CTCAE) version 5.0.

A treatment-emergent adverse event (TEAE) is defined as any event that either occurs after the initiation of study intervention, having been absent at baseline, or, if present at baseline, appears to have worsened in severity or frequency, whether or not the event is considered related to study intervention. A treatment-related adverse event (TRAE) is defined as any TEAE assessed by the Investigator to be ‘Possibly’, ‘Probably’, or ‘Definitely’ related to any study intervention, as well as AEs with missing relationship. An immune-related adverse event (IRAE) is defined as a TRAE that matches a select list of coded preferred terms that have been identified by medical review.

Handling of missing and partial-missing AE dates is described in Section 5.8.1.

The incidence of AEs will be summarized by study intervention group for the following categories:

- All TEAEs
- All TRAEs
- Grade 3-4 TEAEs and TRAEs
- Serious adverse events (SAEs)
- Deaths due to an AE
- AEs leading to treatment discontinuation
- All irAEs

Treatment-emergent and treatment-related AEs will also be summarized by coded preferred Term, system organ class, and severity. In addition, separate summaries will be generated for SAEs.

The following listings will be generated:

- TEAEs
- SAEs
- AEs leading to treatment discontinuation
- Deaths, including primary cause of death

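### The safety analysis has no split at the planned crossover from nivolumab to the combination, so putting a crossover participant in any single group distorts the nivolumab-alone adverse event rates

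*SAP*

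**What the plan says.** Crossover is a planned pathway. Protocol 6.1 says that "participants enrolled on the CD8 high arm in this study could, at disease progression, cross-over to the CD8 low arm". SAP 3 says of the metastatic portion: "At the time of disease progression, participants may crossover to the CD8 low arm or discontinue treatment". The prostate portion allows the same step.

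The safety rules do not mention it:

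- **Grouping.** SAP 5.6, like the Safety Population definition in SAP 5.1 and Protocol 9.2, states: "Participants will be analyzed according to the study intervention actually received". This separates as-treated from as-assigned analysis. It says nothing about two regimens received in sequence.
- **Event window.** SAP 5.6.2 defines a treatment-emergent event as "any event that either occurs after the initiation of study intervention, having been absent at baseline", or worsened if present at baseline. It gives no cut and no second baseline at crossover.
- **Collection.** Under Protocol 8.3.1, events are collected "until 100 days after the last dose of study intervention". After a crossover, that last dose belongs to the second regimen.
- **Tables.** AE incidence (5.6.2), laboratory grades (5.6.3) and vital signs (5.6.4) are summarised by study intervention group. Exposure (5.6.1) is summarised by treatment arm. Neither label is defined for a crossover participant.
- **Relatedness.** SAP 5.6.2 treats an event as treatment-related if it is related to any study drug, and lists no summary by attributed drug.

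SAP 6, which lists differences from the protocol, does not take up the matter.

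**The concern.** Safety and tolerability of nivolumab with or without ipilimumab is the first secondary objective. The nivolumab-alone column should describe toxicity under nivolumab alone, and the plan does not secure that.

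The two regimens are expected to differ. Protocol 2.2.1 reports that "Grade 3 or 4 events occurred in 59% of patients in the nivolumab plus ipilimumab group, in 21% of those in the nivolumab group". Mixing person-time across the crossover can therefore move the monotherapy rate a long way, because the nivolumab group is the small one (about 40 planned, against 160).

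The prostate portion is more exposed. Protocol 6.1 places crossovers in Prostate Cohort A, which stays at 5 participants if Cohort B is judged tolerable (Protocol 6.6.1.4 and 9.1), so one added participant changes that column. The documents do not say how many prostate participants will be CD8 high and so able to cross over.

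**Working it through.** The plan states no figure for the nivolumab-alone AE rate, so there is nothing to reproduce. The check asks what each single-group reading would give.

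**Inputs**
- n = 40 nivolumab participants and 160 combination participants (Protocol 9.1).
- Grade 3-4 risk of 21% on nivolumab and 59% on the combination (Protocol 2.2.1, background figures).
- f, the share of the 40 who cross over. The documents do not give it; 10%, 25% and 50% are assumed.

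**Reading A: crossovers stay in the nivolumab group with all their events**
- If post-crossover risk is independent of earlier events: rate = 0.21 + 0.79 × f × 0.59.
- If a crossover participant's overall risk is 59%: rate = 0.21 + f × (0.59 − 0.21).

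| f | Crossovers | Independent | Overall 59% |
|---|---|---|---|
| 10% | 4 | 0.21 + 0.047 = 25.7% | 0.21 + 0.038 = 24.8% |
| 25% | 10 | 0.21 + 0.117 = 32.7% | 0.21 + 0.095 = 30.5% |
| 50% | 20 | 0.21 + 0.233 = 44.3% | 0.21 + 0.190 = 40.0% |

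With an assumed lower combination risk of 40%, the same formulas give 22.9-24.2%, 25.8-28.9% and 30.5-36.8%.

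**Reading B: crossovers move to the combination group with all their events**
- The combination rate hardly moves. A crossover participant's risk over both periods is 0.21 + 0.79 × 0.59 = 0.676. With 20 crossovers, (160 × 0.59 + 20 × 0.676) / 180 = 60.0% instead of 59%.
- The nivolumab denominator falls from 40 to 36, 30 or 20.
- The rate among those left is 0.21 × (1 − f × r) / (1 − f), where r is the crossovers' nivolumab-period risk relative to the average. With r from 0.5 to 1.25 (assumed), f = 25% gives 24.5% down to about 19%, and f = 50% gives 31.5% down to about 16%. Only at r = 1 does the rate stay at 21%, and then it rests on fewer participants, selected by not having crossed over.

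**Split by period**
If nivolumab events stop at the first ipilimumab dose, the illustrated rate stays at the 21% input for any f, apart from the effect of shorter observation.

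**The case against.** The strongest reply is that the text is silent rather than wrong. Nothing fixes one row per participant; the intervention received can be read period by period, and SAP 5.6.1 counts participants exposed to each intervention, which a crossover participant is twice. A programmer could reach the right split. That stands against any claim that the SAP prescribes misattribution. It does not remove the gap: the split is not required, and in an open-label study the choice could be made after the data are seen.

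A second reply is attribution. Protocol 6.6.1 lets the investigator attribute an event to the combination or to nivolumab alone, and Protocol 9.4.2 plans AEs by attribution. But the SAP supersedes the protocol's analysis plan (Protocol 9.4, SAP 2) and pools relatedness across study drugs. Attribution would also not repair the tables of all treatment-emergent events, Grade 3-4 treatment-emergent events or SAEs.

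The study is exploratory and makes no powered comparison between groups (SAP 5.4). That limits the stakes but does not make the column interpretable.

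A reader might infer two further faults:
- **That the event window never ends.** The definition has no end date, but collection stops 100 days after the last dose. The gap is the missing cut at crossover.
- **That trial-limiting toxicity has the same fault.** Protocol 8.3.7 counts events "during the initial 12 weeks of treatment, unless there is a clear alternative explanation". That limit keeps later post-crossover events out of the nivolumab count, which is the opposite of the AE-table problem. The first scheduled scan is at Cycle 4 Day 1 (3 × 3 = 9 weeks), so a crossover then leaves about 3 weeks inside the window. That overlap does not justify redefining a protocol monitoring rule to which SAP 5.9 only refers.

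**Conclusion.** The point holds as an unspecified rule with material consequences. For a crossover participant the grouping has no unique answer, and either single-group answer distorts the nivolumab-alone column: one adds post-ipilimumab events, the other removes participants and their monotherapy events. It is tempting to conclude that the reported rates will be wrong; the documents support only that they are undefined and open to material bias.

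The size is illustrative. Under reading A the 21% becomes about 25-26%, 31-33% or 40-44% at 10%, 25% or 50% crossover. This rests on an assumed crossover share and on background rates from another trial. The 59% may not carry over: metastatic crossovers receive ipilimumab 1 mg/kg, whereas Protocol 2.2.3 describes the approved melanoma regimen as 3 mg/kg every 3 weeks. Under reading B the combination rate moves by about 1 point at most up to 50% crossover, and the damage is to the nivolumab group's size and composition.

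**What to change.** In SAP 5.6, 5.6.1, 5.6.2, 5.6.3 and 5.6.4, replace participant-level grouping with assignment by treatment period for AEs, exposure, laboratory grades and vital signs:

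1. End the nivolumab period at the first ipilimumab dose.
2. Report events from that dose onward in a separate post-crossover column, with its own denominator and a second baseline at crossover for judging new or worsened events and changes.
3. Do not add crossovers to the CD8-low or Prostate Cohort A columns.
4. Because Protocol 6.6.1.1 says that immune-related events may appear months after dosing, add a sensitivity listing of post-crossover events with onset within 100 days of the last nivolumab-alone dose.

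Leave the 12-week trial-limiting toxicity definition as it is.

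Separately, reconcile the prostate crossover regimen, so that the post-crossover column can be labelled. The Protocol 1.1 synopsis gives ipilimumab 5 mg/kg; the Protocol Figure 3 footnote and SAP 3 and 8.1 give 3 mg/kg, and Protocol 6.1 places crossovers in Prostate Cohort A.

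The period split costs SAP wording and one extra column per safety table; the dates are already collected and no treatment changes. The downsides are that the column will be small and that some late nivolumab events will fall in it, which the listing makes visible.

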### 5.6.1 Exposure to Study Medication

The number of participants exposed to each study intervention and the extent of exposure (as number of doses and cumulative dose received) will be summarized by treatment arm using descriptive statistics. The number of skipped doses will also be summarized by treatment arm.

### 5.6.2 Adverse Events

All reported AEs will be coded using a recent version of the Medical Dictionary for Regulatory Activities (MedDRA) and graded using the NCI Common Terminology Criteria for Adverse Events (CTCAE) version 5.0.

A treatment-emergent adverse event (TEAE) is defined as any event that either occurs after the initiation of study intervention, having been absent at baseline, or, if present at baseline, appears to have worsened in severity or frequency, whether or not the event is considered related to study intervention. A treatment-related adverse event (TRAE) is defined as any TEAE assessed by the Investigator to be ‘Possibly’, ‘Probably’, or ‘Definitely’ related to any study intervention, as well as AEs with missing relationship. An immune-related adverse event (IRAE) is defined as a TRAE that matches a select list of coded preferred terms that have been identified by medical review.

Handling of missing and partial-missing AE dates is described in Section 5.8.1.

The incidence of AEs will be summarized by study intervention group for the following categories:

- All TEAEs
- All TRAEs
- Grade 3-4 TEAEs and TRAEs
- Serious adverse events (SAEs)
- Deaths due to an AE
- AEs leading to treatment discontinuation
- All irAEs

Treatment-emergent and treatment-related AEs will also be summarized by coded preferred Term, system organ class, and severity. In addition, separate summaries will be generated for SAEs.

The following listings will be generated:

- TEAEs
- SAEs
- AEs leading to treatment discontinuation
- Deaths, including primary cause of death

### 5.6.3 Laboratory Data

Clinical laboratory findings will be summarized by the proportion of participants with on-treatment values outside the normal range for each study intervention group.

Select laboratory tests (including but not limited to alanine aminotransferase, albumin, alkaline phosphatase, aspartate aminotransferase, creatinine, platelet count, potassium, sodium, and white blood cells [WBC]) will be graded according to CTCAE version 5.0, and the highest grade per laboratory test per participant will be summarized by study intervention group.

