 - c. Participants who experienced Grade 3 irAEs consisting of laboratory abnormalities that were asymptomatic and have now resolved to \leq Grade 1 or baseline **and** participants who have been off steroid and/or other immunosuppressive therapy, as treatment for irAEs, for ≥ 30 days from Cycle 1, Day 1.
6. Concurrent malignancies are permitted if any one of the following applies:
 - a. Previously treated malignancy for which all treatment of that malignancy was completed at least 2 years before enrollment and no evidence of disease exists, or
 - b. With agreement from the Sponsor and Principal Investigator (PI), participants who have a concurrent malignancy that is clinically stable and does not require tumor-directed treatment are eligible to participate if the risk of the prior malignancy interfering with either safety or efficacy endpoints is very low, or
 - c. With agreement from the Sponsor and PI, other malignancies may be permitted if the risk of the prior malignancy interfering with either safety or efficacy endpoints is very low.

7. Provide newly obtained core needle or incisional biopsy of a non-bone tumor lesion not previously irradiated. Fine needle aspiration is not acceptable.
 - a. Biopsies should be obtained from sites that do not pose significant risk to the participant based on the tumor site and the procedure used. Biopsy sites/procedures including, but not limited to, the brain, open lung/mediastinum, pancreas, or endoscopic procedures extending beyond the esophagus, stomach, or bowel would be considered to pose a significant risk to the participant. Procedures to areas that are deemed by the Investigator to be of non-significant risk based on individual clinical scenarios will be permitted.
8. Measurable disease as defined by RECIST v1.1.
 - a. With the exception of prostate cancer participants enrolled under Amendment 3+ who must have measurable disease, participants who do not have measurable disease by RECIST criteria but whose disease can be objectively measured through tumor markers or another disease-specific standard are considered eligible.
9. Eastern Cooperative Oncology Group (ECOG) performance status of 0 or 1.
10. Aspartate aminotransferase (AST) and alanine aminotransferase (ALT) ≤ 3 x upper limit of normal (ULN).
 - a. Participants with hepatocellular carcinoma (HCC) may be eligible provided they have AST and ALT that are ≤ 5.0 x ULN.
11. Hemoglobin ≥ 9 g/dL.
12. Total bilirubin $\leq 1.5 \times$ ULN.

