### 5.3 Analysis of Baseline Characteristics

Demographic and baseline characteristics of the study population will be summarized overall and for each study intervention group. Variables to be summarized include, but are not limited to, age, sex, race, ethnicity, Eastern Cooperative Oncology Group (ECOG) performance status, cancer location, stage at initial diagnosis, prior lines of systemic cancer therapy, and CD8 percentage at screening.

The baseline value of any variable will be defined as the last value recorded on or before the date of first administration of study intervention.

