### 5.6.4 Vital Signs

Vital signs at each visit and change from baseline to each visit will be summarized using descriptive statistics for each study intervention group. The baseline value of any variable will be defined as the last value recorded prior to the first administration of study intervention. Participants with a missing baseline value will not be summarized for that variable.

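### Neither laboratory summary in SAP 5.6.3 is referred to baseline, so abnormalities present at entry can be reported as on-treatment findings

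*SAP*

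**What the plan says.** SAP 5.6.3 contains two laboratory summaries. The first is the proportion of participants with "on-treatment values outside the normal range for each study intervention group". The second applies to a selection of tests graded under CTCAE v5.0, for which "the highest grade per laboratory test per participant will be summarized by study intervention group". Neither sentence mentions baseline. The section has no change from baseline, no shift table and no treatment-emergent definition for laboratory values, and it does not define the on-treatment window.

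Other parts of the SAP do use baseline. Under SAP 5.6.2 an event already present counts as treatment-emergent only if it "if present at baseline, appears to have worsened in severity or frequency". SAP 5.6.4 says: "Vital signs at each visit and change from baseline to each visit will be summarized". SAP 5.3 supplies a general rule: "The baseline value of any variable will be defined as the last value recorded on or before" the date of first dosing.

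Protocol 5.1 admits participants with AST and ALT up to 3 x ULN (5 x in HCC), bilirubin up to 1.5 x ULN (higher limits in HCC and Gilbert syndrome), hemoglobin from 9 g/dL, platelets from 75 x 10^9/L and creatinine clearance from 30 mL/min.

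**The concern.** A participant who enters with AST at 2.5 x ULN and stays there throughout is counted as having an on-treatment abnormality. The grade carried in from entry can also be reported as that participant's highest grade. The tables then mix underlying disease, chance excursions and drug effect.

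No group in this study is untreated, so each participant's own baseline is the only internal reference for a drug effect on laboratory values. Safety is a secondary objective, and SAP 5.6 names laboratory parameters as one of its components. At stake is whether a reader of the laboratory tables can tell what was there before treatment from what appeared or worsened on it.

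**Working it through.** The plan states no figure on this point, so there is nothing to reproduce. The calculation below only shows the possible size.

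**Inputs from the documents.** On-treatment hematology and chemistry draws in the Protocol 1.3 schedules: 8 in Table 1 (Cycle 1 Day 8, then Cycles 2 to 8), 10 in Table 2 (Cycle 1 Day 8, then Cycles 2 to 10), and 4 by Cycle 2 Day 22 in Table 4, then every cycle.

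**Assumed, not in the documents.** Chance q that a single test is out of range with no drug effect: 1% to 5%. Share b abnormal at entry: 10% to 50%. Within-person correlation of repeat tests. The eligibility limits are bounds and say nothing about how common abnormal values are.

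**Step 1, repeat testing alone.** With independent tests, P(at least one out of range in k tests) = 1 − (1 − q)^k.
- k = 8: 7.7%, 18.3% and 33.7% for q = 1%, 2.5% and 5% (for example 1 − 0.95^8 = 0.337).
- k = 4 and k = 10 at q = 5%: 18.5% and 40.1%.

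**Step 2, adding entry abnormalities that persist.** Share flagged = b + (1 − b) × P.
- b = 20%, q = 2.5%, k = 8: 0.20 + 0.80 × 0.183 = 34.7%, against 18.3% among those normal at entry.
- b = 30%, q = 5%, k = 10: 0.30 + 0.70 × 0.401 = 58.1%, against 40.1%.
- Range for q = 2.5%, k = 8: 26.5% at b = 10% and 59.2% at b = 50%.

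**Step 3, correlated repeats, by simulation with no drug effect.** Each value is a person effect plus visit error with total SD 1. The normal range is ±1.96 SD. The population mean is either centred or shifted by 1.5 SD. The shift puts 1 − Φ(1.96 − 1.5) = 1 − Φ(0.46) = 32% outside the range at entry. Results with 8 on-treatment tests:

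| Population | Correlation | Flagged, all | Flagged, normal at entry |
|---|---|---|---|
| Centred | 0.7 | 19% | 16% |
| 32% abnormal at entry | 0.7 | 64% | 49% |
| 32% abnormal at entry | 0.85 | 54% | 33% |

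**Step 4, how much of the total comes from entry.** With 68% normal at entry, those newly out of range are 0.68 × 0.49 = 33 points of the 64, which leaves 31 points (31/64 = 48%) from participants already abnormal at entry. At correlation 0.85 the split is 0.68 × 0.33 = 22 of 54, which leaves 32 points (32/54 = 59%).

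**Step 5, what a baseline restriction does not remove.** With 32% abnormal at entry and correlation 0.7, going from 8 to 16 tests raises the overall figure from 64% to 72%. It raises the figure among those normal at entry from 49% to 59%. The dependence on number of visits remains.

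**The case against.** The strongest reply is that laboratory changes that matter clinically are already judged against baseline. Protocol 10.5.5 makes a laboratory value an adverse event if it comes with symptoms, changes study treatment, leads to medical intervention or a medication change, or is judged clinically significant. Those events enter the treatment-emergent tables of SAP 5.6.2 by preferred term and severity. This stands, and it limits the point. A reader might infer that the SAP never relates laboratory safety to baseline; the documents do not support that. What remains is the systematic table, which should show what the reporting filter misses.

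Other stronger readings also fail:
- The out-of-range proportion is not the only laboratory summary. The worst-grade summary separates mild from severe excursions, although no baseline reference is stated for it. Counting a participant on any single out-of-range value is the natural reading of SAP 5.6.3, but the text does not spell it out.
- It would be too much to say that laboratory tests alone lack a baseline comparison. SAP 5.4.3.1 summarises PSA as change from baseline, as an efficacy measure. Nor are all adverse event categories in SAP 5.6.2 explicitly limited to treatment-emergent events.
- A reader might expect a baseline-referenced table to cure the effect of repeat testing. Step 5 shows that it does not.
- The same simulation with independent visits and 32% abnormal at entry flags 96%. At zero correlation, baseline predicts nothing about later values, so that figure cannot illustrate carry-over from entry and is not relied on.

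Whether CTCAE v5.0 grading of a given test already allows for an abnormal baseline cannot be settled from these documents. The SAP does not say.

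Finally, the study is exploratory. SAP 5.4 says it is not intended for comparisons between groups, and SAP 5.6.1 reports exposure by arm. That makes the consequence small, but it does not supply the missing reference.

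**Conclusion.** The point holds as a minor gap in safety reporting. As written, both summaries in SAP 5.6.3 can present abnormalities or grades that existed at entry as on-treatment findings, and the eligibility criteria make such values likely. Under the stated assumptions, participants already abnormal at entry make up about half to three fifths of those flagged when there is no drug effect at all. That size rests on the assumed 32% abnormal at entry, correlations of 0.7 to 0.85 and 8 tests; with few abnormal at entry the difference is small (19% against 16% in the centred case). The direction does not depend on these choices where abnormal entry values persist.

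The primary endpoints are untouched. So are the stopping rules, because the trial-limiting toxicity in Protocol 8.3.7 and the discontinuation counts for the prostate cohorts in Protocol 6.6.1.4 rest on adverse events leading to discontinuation, not on these tables.

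**What to change.** In SAP 5.6.3:
1. Report the proportion of participants whose CTCAE grade worsens from baseline on treatment. For ungraded tests, report those normal at baseline who become abnormal on treatment.
2. Present the highest grade as a shift table of baseline grade by worst on-treatment grade.
3. Use the last value before first dose as baseline, and define the on-treatment window. SAP 5.3 accepts a value on the date of first dosing, while SAP 5.6.4 requires one before it. Some screening procedures may fall on Cycle 1 Day 1 (Protocol 1.3, Table 1, footnote a), so the two wordings need reconciling.
4. The existing out-of-range summary may stay beside these tables.
5. Add a note that all these figures rise with the number of visits and should be read with the exposure reported under SAP 5.6.1.

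The cost is a little programming. Screening hematology and chemistry are already scheduled in every arm. Participants without a baseline value drop out of the shift table, as SAP 5.6.4 already accepts for vital signs.
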